6.3 Missing Data Imputation

No data will be imputed for any efficacy or safety analyses except for analyses of the HCV RNA endpoints.

HCV RNA values will be selected for the SVR₁₂ analysis based on defined visit windows. When there is no HCV RNA value in a visit window based on defined visit windows, the closest values before and after the window, regardless of the value chosen for the subsequent and preceding window, will be used for the flanking imputation described below.

If a subject has a missing HCV RNA value at a post-Day 1 visit, but with undetectable or unquantifiable HCV RNA levels at both the preceding value and succeeding value, the HCV RNA level will be considered undetectable or unquantifiable, respectively, at this visit for this subject. For SVR₁₂ analysis, if there is no value in the appropriate window

after flanking imputation but there is an HCV RNA value after the window, then it will be imputed into the SVR₁₂ window. Similarly, for SVR₂₄ analysis, if there is no value in the appropriate window after flanking imputation but there is HCV RNA value after the window, then it will be imputed into the SVR₂₄ window.

If a subject starts another treatment for HCV, then all HCV RNA and PRO values for this subject measured on or after the start date of the new HCV treatment will be excluded from analyses. The subject will be considered a failure for summaries of viral response at all time points after the start of the new HCV treatment.

HCV RNA < LLOQ Analyses for SVR

If a subject is missing an HCV RNA value for the visit window associated with the analysis of SVR after performing the imputations described above, then this value will be imputed with an HCV RNA value from a local laboratory if present; otherwise, the HCV RNA value for this visit will be missing. Subjects with missing HCV RNA data in the analysis window, after imputations, will be imputed as a failure.

HCV RNA Analyses for Relapse and Virologic Failure

If HCV RNA values from the central laboratory are missing but a local laboratory value is present in the appropriate time period, then the local laboratory value will be used to assess post-treatment relapse and on-treatment virologic failure.

Missing Data Imputation for PRO Questionnaires

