9.0 Study Drug Exposure and Compliance

9.1 Exposure

The duration of exposure to study drug will be summarized in the safety population. Duration of exposure is defined for each subject as the last study drug dose date minus the first study drug dose date plus 1 day.

The safety population will be used to summarize the duration of exposure for each treatment arm.

Descriptive statistics (mean, standard deviation, median, minimum, and maximum) will be presented. Study drug duration also will be summarized with frequencies and percentages using the following categories:

- 1 to 15 days
- 16 to 30 days
- 31 to 45 days
- 46 to 60 days
- 61 to 75 days
- 76 to 90 days
- > 90 days

In addition, the number and percentage of subjects with a study drug duration of ≥ 77 days for Arm A, B, E and F, ≥ 49 days for Arm C, and ≥ 38 days for Arm D will be summarized.

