10.0 Efficacy Analysis

10.1 General Considerations

Analyses will be performed on the intent-to-treat (ITT) population. Sensitivity analyses of the primary endpoint, when applicable, will be performed on the mITT-GT-VF population specified in Section 5.1.1.

Missing data will be imputed as described in Section 6.3 for analyses of the HCV RNA endpoints of SVR.

Plasma HCV RNA levels will be determined for each sample collected by the central laboratory using the Roche COBAS TaqMan® real-time reverse transcriptase-PCR (RT-

PCR) assay v.2.0. For this assay, the lower limit of quantitation (LLOQ) is 25 IU/mL regardless of genotype, and the lower limit of detection (LLOD) varies by genotype. For GT3, the lower limit of detection (LLOD) is 20 IU/mL; for GT2, LLOD is 20 IU/mL. HCV RNA results that are detectable but not quantifiable are reported as "< 25 IU/mL HCV RNA detected" and those that are undetectable are reported as "HCV RNA not detected" in the database.

The notation "HCV RNA < LLOQ" is used to represent all HCV RNA values < 25 IU/mL, including values reported as "HCV RNA not detected" or "< 25 IU/mL HCV RNA detected." HCV RNA \geq LLOQ are all quantifiable values of 25 IU/mL or greater.

IL28B rs12979860 will be resulted as C/C, C/T, or T/T by the central laboratory.

Definitions for Efficacy Endpoints

Note that a confirmed quantifiable post-treatment value is defined as two consecutive post-treatment HCV RNA measurements \geq LLOQ. During treatment, a confirmed quantifiable value is defined as any two consecutive HCV RNA values \geq LLOQ, either both during treatment or at the final treatment measurement and the next consecutive post-treatment measurement.

Breakthrough = confirmed HCV RNA \geq LLOQ after HCV RNA < LLOQ during treatment, or confirmed increase from nadir in HCV RNA (two consecutive HCV RNA measurements $> 1 \log_{10}$ IU/mL above nadir) at any time point during treatment. A single breakthrough value (\geq LLOQ or $> 1 \log_{10}$ IU/mL above nadir) followed by lost to follow-up will be considered a breakthrough (i.e., will not require confirmation).

On-treatment virologic failure = breakthrough or failure to suppress during treatment (all on-treatment values of HCV RNA \geq LLOQ) with at least 6 weeks (defined as study drug duration \geq 36 days) of treatment for 12-week and 8-week treatment or at least 26 days of treatment for 6-week treatment.

RVR (rapid virologic response) = HCV RNA < LLOQ in the Week 4 window.

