EOTR (end of treatment response) = HCV RNA < LLOQ in the Week 12 window for 12-week regimen, Week 8 window for 8-week regimen, and Week 6 for 6-week regimen.

SVR₄ = HCV RNA < LLOQ in the SVR₄ window (4 weeks after the last actual dose of study drug) without any confirmed quantifiable (\geq LLOQ) post-treatment value before or during that SVR window.

SVR₁₂ = HCV RNA < LLOQ in the SVR₁₂ window (12 weeks after the last actual dose of study drug) without any confirmed quantifiable (\geq LLOQ) post-treatment value before or during that SVR window.

SVR₂₄ = HCV RNA < LLOQ in the SVR₂₄ window (24 weeks after the last actual dose of study drug) without any confirmed quantifiable (\geq LLOQ) post-treatment value before or during that SVR window.

Relapse₁₂ = confirmed HCV RNA \geq LLOQ between end of treatment and 12 weeks after last actual dose of active study drug (up to and including the SVR₁₂ assessment time point) for a subject with HCV RNA < LLOQ at Final Treatment Visit who completes treatment, excluding re-infection as described below.

Relapse₂₄ = confirmed HCV RNA \geq LLOQ during SVR₂₄ window among subjects who achieved SVR₁₂ and have data available during the SVR₂₄ window, excluding re-infection.

Relapse_{late} = confirmed HCV RNA \geq LLOQ at any time after the SVR₂₄ assessment time point for a subject who achieved SVR₂₄ and has post-SVR₂₄ HCV RNA data available, excluding re-infection.

Relapse_{overall} = confirmed HCV RNA \geq LLOQ between end of treatment and up to and including the last HCV RNA measurement collected in the PT Period for a subject with HCV RNA < LLOQ at Final Treatment Visit who completes treatment. Completion of treatment is defined as a study drug duration \geq 37 days, \geq 49 days and \geq 77 days for planned treatment duration of 6 week, 8 weeks and 12 week, respectively. Also, include a

summary of Relapse_{overall} for subjects who prematurely discontinued treatment, excluding re-infection.

For relapse analyses, the completion of treatment is defined as above. If the last available post-treatment value is \geq LLOQ, then the subject will be considered a relapse (i.e., will not require confirmation). Relapse analyses will exclude subjects who do not have any post-treatment HCV RNA values.

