HCV re-infection is defined as confirmed HCV RNA \geq LLOQ after the end of treatment in a subject who had HCV RNA $<$ LLOQ at Final Treatment Visit, along with the post-treatment detection of a different HCV genotype, subtype, or clade compared with baseline, as determined by phylogenetic analysis of the NS3 or NS5A, and/or NS5B gene sequences. Re-infection in the case of the same HCV subtype is defined as a clade switch, as indicated by the lack of clustering between the baseline and post-treatment sequences by phylogenetic analysis. If phylogenetic analysis is not possible due to technical difficulties, HCV re-infection may be determined with a confirmed HCV genotype or subgenotype switch by the Versant HCV Genotype Inno-LiPA Assay v2.0 or Sanger assay.

Reasons for SVR₁₂ Non-Response

Subjects who do not achieve SVR₁₂ (SVR₁₂ non-responders) will be categorized as having:

1. On-treatment virologic failure (see **On-treatment virologic failure** definition);
2. Relapse (defined according to the **Relapse₁₂** definition for subjects who complete treatment);
3. Prematurely discontinued study drug with no on-treatment virologic failure (defined as any SVR₁₂ non-responder who prematurely discontinued study drug (duration $<$ 77 days, $<$ 49 days, and $<$ 38 days for 12 week, 8 week, and 6 week treatment regimens) and did not meet the **On-treatment virologic failure definition**);

4. HCV re-infection (see definition described earlier);
5. Missing follow-up data in the SVR₁₂ window (defined as any subject who completed study drug without data in the SVR₁₂ window and not meeting the definitions of [1], [2], [3], or [4]);
6. Other (defined as any SVR₁₂ non-responder not meeting the definitions of [1] – [5], such as a subject with a single quantifiable value within the SVR₁₂ window followed by an undetectable value beyond the SVR₁₂ window).

Reasons for SVR₂₄ Non-Response

Subjects who do not achieve SVR₂₄ (SVR₂₄ non-responders) will be categorized as having:

1. On-treatment virologic failure (see **On-treatment virologic failure definition**);
2. Relapse (defined according to the **Relapse₁₂** definition for subjects who complete treatment);
3. Relapsed after achieving SVR₁₂ (see **Relapse₂₄**);

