4. Prematurely discontinued study drug with no on-treatment virologic failure (defined as any SVR₂₄ non-responder who prematurely discontinued study drug [duration < 154 days] and did not meet the **On-treatment virologic failure**, **Relapse₁₂**, or **Relapse₂₄** definitions);
5. HCV re-infection;
6. Missing follow-up data in the SVR₂₄ window (defined as any subject who completed study drug without data in the SVR₂₄ window, and not meeting the definitions of [1], [2], [3], [4], or [5]);
7. Other (defined as any SVR₂₄ non-responder not meeting the definitions of [1] – [6]).

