The number of completers (defined as study drug duration \geq 77 days, \geq 49 days, \geq 38 days for 12-week, 8-week, 6-week of treatment, respectively) with final on treatment HCV RNA $<$ LLOQ who relapse within the SVR₄ window, within the SVR₁₂ window, within the SVR₂₄ window (defined in [Table 5](#)), and anytime post-treatment (study drug end day \geq 3) will be summarized along with a corresponding listing displaying the first occurrence of relapse. A similar table and listing will be provided of Preterm Relapses for subjects who do not complete treatment (defined as study drug duration $<$ 77 days, $<$ 49 days, $<$ 38 days for 12-week, 8-week, 6-week of treatment, respectively) with HCV RNA $<$ LLOQ at the Final Treatment visit.

The concordance between SVR₁₂ and SVR₂₄ will be assessed by agreement between SVR₁₂ and SVR₂₄ and by the positive predictive value (PPV) and the negative predictive value (NPV) of SVR₁₂ on SVR₂₄. The agreement between SVR₁₂ and SVR₂₄ is defined as the number of subjects achieving both SVR₁₂ and SVR₂₄ and the number of subjects not achieving both SVR₁₂ and SVR₂₄ out of all subjects in the ITT population. The PPV of SVR₁₂ on SVR₂₄ is the proportion of subjects who achieve SVR₂₄ out of all subjects who achieved SVR₁₂. The NPV of SVR₁₂ on SVR₂₄ is the proportion of subjects who do not achieve SVR₂₄ out of all subjects who do not achieve SVR₁₂.

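### The SVR₂₄ non-response reasons use a 154-day discontinuation cut that fits no regimen, so completers meet the premature-discontinuation category and the missing-data and other categories are always empty

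*SAP*

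**What the plan says.** SAP 10.1 sorts SVR₂₄ non-responders into seven categories. Category 4, premature discontinuation, is a non-responder "who prematurely discontinued study drug [duration < 154 days] and did not meet the" definitions of on-treatment virologic failure, Relapse₁₂ or Relapse₂₄. One cut serves all arms. Category 5 is re-infection. Category 6 is "any subject who completed study drug without data in the SVR₂₄ window", provided none of categories 1 to 5 applies. Category 7 takes whoever meets none of categories 1 to 6.

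The SVR₁₂ list in the same section has the same structure but sets premature discontinuation at under 77, under 49 and under 38 "days for 12 week, 8 week, and 6 week treatment regimens". SAP 9.1 tabulates subjects "with a study drug duration of ≥ 77 days for Arm A, B, E and F, ≥ 49 days for Arm C", and 38 days or more for Arm D. SAP 10.4, 10.6 and 10.7 also use 77/49/38.

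Two related definitions differ among themselves:

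- **Completion of the 6-week regimen.** The relapse definitions in SAP 10.1 contain the sentence beginning "Completion of treatment is defined as a study drug duration", which sets 37 days for this regimen. The sections above use 38.
- **Failure to suppress.** SAP 10.1 and 10.4 require 36 days of drug for the 12- and 8-week regimens, "or at least 26 days of treatment for 6-week treatment". The tabulation in SAP 10.6 uses a flat 38 days.

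**The concern.** A cut meant to separate early stoppers from completers has to lie a little below the planned course. At 154 days it lies far above every course in the trial, so it cannot tell the two groups apart. The list also contradicts itself: category 6 is written for completers, yet every completer who could reach it is already in category 4.

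The reasons for missing SVR₂₄ are a listed additional efficacy endpoint for each arm (SAP 10.6, Protocol 8.1.2.3). A subject who finished treatment and was then lost to follow-up would appear in this table as having stopped drug early, while the exposure summary and the SVR₁₂ reasons treat the same subject as a completer. In arms this small a reader looks at individual cases, and that label points towards a treatment problem that did not occur.

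**Working it through.** **Inputs**

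- Planned treatment: 12 weeks (Arms A, B, E, F), 8 weeks (Arm C), 6 weeks (Arm D), from SAP 4.1 and 4.2.
- Upper ends of the last on-treatment windows: Study Days 98, 70 and 49, from SAP Tables 2, 3 and 4.
- Duration: last dose date minus first dose date plus 1, from SAP 9.1.
- Post-treatment windows: SVR₂₄ is Study Drug End Days 127 to 210; Post-Treatment Weeks 36 and 48 are 211 to 294 and 295 to 378, from SAP Table 5.

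**Can 154 be reproduced from the design?** No.

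- 154/7 = 22 weeks.
- Planned courses: 12 × 7 = 84, 8 × 7 = 56, 6 × 7 = 42 days.
- Excess over plan: 154 − 84 = 70, 154 − 56 = 98, 154 − 42 = 112 days.
- Excess over the widest on-treatment window: 154 − 98 = 56 days.

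Protocol 5.5.6 says interruptions should not exceed 7 consecutive days, so ordinary delays would not stretch a course to 154 days. The figure would suit a 24-week course, since 154/168 = 77/84 = 0.917, but no arm has one. That origin is only a guess: the other cuts do not keep this fraction (49/56 = 0.875, 38/42 = 0.905), and the documents do not explain the number.

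**Which categories can be filled?** Take completers with no on-treatment failure, Relapse₁₂ or Relapse₂₄, from the completion cut to the end of the last window. That gives 22 day values for the 12-week regimen (77 to 98), 22 for the 8-week (49 to 70) and 12 for the 6-week (38 to 49). Each day value has four profiles: re-infected or not, SVR₂₄ data missing or not. These are logical profiles, not expected subjects.

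| Completer profiles (12 / 8 / 6 weeks) | Cut at 154 | Cuts at 77/49/38 |
|---|---|---|
| Meet category 4 | 88 / 88 / 48 | 0 / 0 / 0 |
| Meet category 5 (re-infection) | 44 / 44 / 24 | 44 / 44 / 24 |
| Meet category 6 (missing) | 0 / 0 / 0 | 22 / 22 / 12 |
| Meet category 7 (other) | 0 / 0 / 0 | 22 / 22 / 12 |

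The first row is 22 × 4 = 88, 22 × 4 = 88 and 12 × 4 = 48. With the 154-day cut, the re-infected completers meet categories 4 and 5 together.

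**Who would be mislabelled?**

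1. *Completers with missing data.* SAP 6.3 keeps this group small. If the SVR₂₄ window is still empty after flanking imputation "but there is HCV RNA value after the window, then it will be imputed into the SVR₂₄ window", so any usable central value from day 127 onward either lies in the window or can fill it. What remains is a completer with no such value at Post-Treatment Weeks 24, 36 or 48 and no local-laboratory value.
2. *Completers with an isolated quantifiable value.* The SVR₂₄ window uses the last value in it. A completer whose last in-window value is a single quantifiable result, followed by a later value below LLOQ, fails SVR₂₄ without a confirmed relapse. The SVR₁₂ list gives this kind of case as its example of other.

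One subject is 1/10 = 10 percentage points of a 10-subject arm, or 1/20 = 5 points of Arm E.

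**Minor mismatches.** The 37/38-day difference affects only an Arm D subject with exactly 37 days of drug. The flat 38-day cut in SAP 10.6 leaves out never-suppressed subjects with 36 or 37 days (12- and 8-week regimens) or 26 to 37 days (6-week regimen), whom 10.1 and 10.4 count as on-treatment failures.

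**The case against.** The best defence is that the bracket merely annotates subjects who really did stop early, as recorded on the eCRF. Completers would then stay out of category 4, and categories 6 and 7 would work. This is a possible reading, but it does not save the text. The parallel SVR₁₂ wording uses its bracket as the definition, and the SAP defines completion by duration in 10.1, 10.4 and 10.6. The bracket is the only operational rule given, and on the eCRF reading the 154-day cut would do nothing. The number needs correcting either way.

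Two other points stand. The effect is small: one descriptive table, possibly with no affected subjects, while disposition and exposure are reported separately. And re-infection overlap is not caused by the 154-day cut alone. Category 4 does not exclude re-infection and the list states no order of precedence, so an early stopper who is re-infected would still meet both categories after the correction. The SVR₁₂ list has the same overlap.

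The 37/38-day and failure-to-suppress mismatches are separate drafting points and add nothing to the weight of this one.

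**Conclusion.** The concern holds. The 154-day cut matches no regimen and contradicts the cuts used elsewhere in the SAP. Taking the bracket as the definition of premature discontinuation, every SVR₂₄ non-responder without on-treatment failure, Relapse₁₂ or Relapse₂₄ meets category 4, and categories 6 and 7 cannot be filled in any arm. This assumes only that nobody's duration reaches 154 days.

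The consequence is misclassification in the table of SVR₂₄ non-response reasons. No response or relapse rate depends on the 154-day cut. The number of affected subjects is unknown and probably small. It is still a stated rule for a listed endpoint that gives wrong labels if programmed as written, so it should be corrected before that table is produced.

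**What to change.** In SAP 10.1, SVR₂₄ category 4, replace the 154-day cut with under 77, under 49 and under 38 days for the 12-, 8- and 6-week regimens, as in the SVR₁₂ reasons. This costs some SAP wording and one programming constant and changes no response or relapse rate.

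In the same revision:

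- Change the 37-day completion cut for the 6-week regimen in 10.1 to the 38 days used elsewhere. The documents give no rationale for either figure; 38 is the prevailing one. The Arm D relapse denominator could change only for a subject with exactly 37 days of drug.
- Align the failure-to-suppress tabulation in 10.6 with 10.1 and 10.4: at least 36 days for the 12- and 8-week regimens and at least 26 days for the 6-week regimen. Do not impose one cut throughout. This can add subjects to that tabulation, but leaves the secondary on-treatment failure endpoint as defined.
- Preferably state which category takes precedence when a re-infected subject also stopped drug early, in both the SVR₁₂ and SVR₂₄ lists.

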10.2 Handling of Multiplicity

No multiplicity issue applicable in this study.

10.3 Primary Efficacy Analysis

The primary endpoint is the percentage of subjects with SVR₁₂ (HCV RNA < LLOQ 12 weeks after the last actual dose of study drugs). The number and percentage of subjects achieving SVR₁₂ will be calculated for each treatment arm and 2-sided 95% Wilson score confidence intervals for a binomial proportion will be computed by treatment arm.

10.4 Secondary Efficacy Analyses

The secondary efficacy endpoints are:

- The percentage of subjects in each treatment arm and across all treatment arms with on-treatment virologic failure (breakthrough defined as confirmed HCV RNA \geq LLOQ after HCV RNA < LLOQ during treatment, or confirmed increase from nadir in HCV RNA at any time point during treatment, or failure to suppress during treatment (all on-treatment values of HCV RNA \geq LLOQ) with at least 6 weeks (defined as active study drug duration \geq 36 days) of treatment for 12-week and 8-week treatment or at least 26 days of treatment for 6-week treatment.
- The percentage of subjects with post-treatment relapse (relapse₁₂ defined as confirmed HCV RNA \geq LLOQ between end of treatment and 12 weeks after last actual dose of active study drug (up to and including the SVR₁₂ assessment time point) for a subject with HCV RNA < LLOQ at Final Treatment Visit who completes treatment. Completion of treatment is defined as study drug duration \geq 77 days, 49 days and 38 days for 12-week, 8-week, and 6-week of treatment, respectively.

The numbers and percentages of the subjects with virologic failure during treatment and with post-treatment relapse will be calculated for each arm. The corresponding 2-sided 95% Wilson score confidence intervals for a binomial proportion will be calculated.

10.5 Sensitivity Analysis

A sensitivity analysis for the primary efficacy endpoint as described in Section 10.3 will be conducted using mITT-GT-VF population defined in Section 5.1.1.

10.6 Additional Efficacy Analyses

The following additional efficacy endpoints will be summarized and analyzed for each treatment arm:

- All reasons for not achieving SVR₁₂ for subjects who do not achieve SVR₁₂;
- Number and percentage with unquantifiable HCV RNA at each post-baseline visit throughout the Treatment Period (using data from the central laboratory as observed, i.e., no imputation for missing data);
- The percentage of subjects with HCV RNA < LLOQ 24 weeks after the last actual dose of study drug (SVR₂₄);
- All reasons for not achieving SVR₂₄ for subjects who do not achieve SVR₂₄.
- Time to suppression of HCV RNA (defined as the study day of the first of two successive HCV RNA < LLOQ) during the Treatment Period.

In the above analyses that use the number and percentage of responders, the rates and 2-sided 95% Wilson score confidence interval for a binomial proportion will be calculated.

For HCV RNA levels, the time to suppression during treatment will be calculated for each subject, and the median time will be estimated using Kaplan-Meier methodology for right censored observations.

Imputations for missing data will be performed as described in Section 6.3 for analyses of SVR, RVR, and EOTR where a missing response will be imputed as a failure after performing the described imputation. All other endpoints will be presented using data as observed.

The number and percent of subjects who fail to suppress HCV RNA and received at least 6 weeks of treatment (active study drug duration \geq 38 days) will be tabulated along with the subject numbers corresponding to the subjects who failed to suppress.

The number of subjects who breakthrough at any time during treatment and within each protocol-specified visit (defined in [Table 2](#), [Table 3](#), and [Table 4](#)) will be summarized along with a corresponding listing displaying the subject numbers at the first occurrence of breakthrough.

The number of completers (defined as study drug duration \geq 77 days, \geq 49 days, \geq 38 days for 12-week, 8-week, 6-week of treatment, respectively) with final on treatment HCV RNA $<$ LLOQ who relapse within the SVR₄ window, within the SVR₁₂ window, within the SVR₂₄ window (defined in [Table 5](#)), and anytime post-treatment (study drug end day \geq 3) will be summarized along with a corresponding listing displaying the first occurrence of relapse. A similar table and listing will be provided of Preterm Relapses for subjects who do not complete treatment (defined as study drug duration $<$ 77 days, $<$ 49 days, $<$ 38 days for 12-week, 8-week, 6-week of treatment, respectively) with HCV RNA $<$ LLOQ at the Final Treatment visit.

The concordance between SVR₁₂ and SVR₂₄ will be assessed by agreement between SVR₁₂ and SVR₂₄ and by the positive predictive value (PPV) and the negative predictive value (NPV) of SVR₁₂ on SVR₂₄. The agreement between SVR₁₂ and SVR₂₄ is defined as the number of subjects achieving both SVR₁₂ and SVR₂₄ and the number of subjects not achieving both SVR₁₂ and SVR₂₄ out of all subjects in the ITT population. The PPV of SVR₁₂ on SVR₂₄ is the proportion of subjects who achieve SVR₂₄ out of all subjects who achieved SVR₁₂. The NPV of SVR₁₂ on SVR₂₄ is the proportion of subjects who do not achieve SVR₂₄ out of all subjects who do not achieve SVR₁₂.

